3.8.2. Efficacy Analysis

The following endpoints will be used to evaluate durability of treatment effect and summarized by treatment sequence and overall for FAS population:

- Change from baseline in PANSS total score, and subscale scores (positive, negative, and general psychopathology subscales) by visit
- Change from baseline in PANSS Excited Component (EC) score (comprised of 5 items, P4. excitement, G4. tension, P7. hostility, G8. uncooperativeness, and G14. poor impulse control) by visit
- Change from baseline in PANSS Marder factor scores by visit
- Change from baseline in CGI-S by visit
- Proportion of Subjects with PANSS response ($\geq 30\%$ improvement from baseline in PANSS total score)
- Time to first relapse
- Time to first remission
- Time to discontinuation

In general, continuous and categorical endpoints will be summarized using descriptive statistics by treatment sequence and overall. Change from baseline within the treatment sequence and overall may also be tested using an one-sample t-test.

The PANSS Marder factor model² consisted of the following 5 factors:

- Negative symptoms
 - N1. blunted affect
 - N2. emotional withdrawal
 - N3. poor rapport
 - N4. passive social withdrawal
 - N6. lack of spontaneity
 - G7. motor retardation
 - G16. active social avoidance
- Positive symptoms
 - P1. delusions
 - P3. hallucinatory behavior
 - P5. grandiosity
 - P6. suspiciousness
 - N7. stereotyped thinking
 - G1. somatic concern
 - G9. unusual thought content
 - G12. lack of judgment and insight
- Disorganized thought
 - P2. conceptual disorganization
 - N5. difficulty in abstract thinking
 - G5. mannerisms and posturing
 - G10. disorientation
 - G11. poor attention
 - G13. disturbance of volition
 - G15. preoccupation
- Uncontrolled hostility/excitement
 - P4. excitement
 - P7. hostility

- G8. uncooperativeness
- G14. poor impulse control
- Anxiety/depression
 - G2. anxiety
 - G3. guilt
 - G4. tension
 - G6. depression

Stabilization is defined as meeting all of the following stabilization criteria:

- PANSS total score ≤ 80
- PANSS score ≤ 4 on each of the following items:
 - P2: conceptual disorganization
 - P3: hallucinatory behavior
 - P6: suspiciousness
 - G9: unusual thought content

After a subject achieves stabilization, relapse and remission are defined as following:

- Relapse: $\geq 30\%$ increase in PANSS total score or re-hospitalization for psychotic symptoms.
- Remission: PANSS score ≤ 3 (mild or less) on each of the following items in two consecutive efficacy assessments
 - P1: delusions
 - G9: unusual thought content
 - P3: hallucinatory behavior
 - P2: conceptual disorganization
 - G5: mannerisms/posturing
 - N1: blunted affect
 - N4: social withdrawal
 - N6: lack of spontaneity

Time to first relapse will be estimated using the Kaplan-Meier method by treatment sequence and overall. It is defined as the time from the date of stabilization to the date of first relapse. Subjects who completed the treatment without relapse will be censored at the date of last dose. Time to first remission will be analyzed similarly.

Time to treatment discontinuation will be analyzed similarly using the Kaplan-Meier method by treatment sequence and overall. Both all cause discontinuation and discontinuation due to AE will be summarized. For prematurely discontinued subjects (all cause or due to AE), time to event is defined as time from the date of first dose of study drug to the date of last dose of study drug. Other subjects will be censored at the last dose of the study drug.

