8.2. Schedule of Visits and Assessments

The schedule of assessments is shown in Table 3.

A visit window of ± 2 days is permitted throughout the Treatment Period and the Follow-up Period (Visits 2-30). For a missed visit, the site should attempt to contact the subject to reschedule.

Premature discontinuation procedures are provided in Section 7.3.

On Day 3, study staff will check in with outpatient subjects by phone to determine if a dose increase to ALKS 3831 15/10 or 20/10 is needed. If, in the opinion of the Investigator, a dose increase is warranted, an Unscheduled Visit will be arranged mid-Week 1. The following procedures will be performed during the Unscheduled Visit: study drug return, adherence review, and study drug dispensation.

Dose adjustments can only occur on-site and require subjects to come to the study center. Throughout the study, subjects requiring dose adjustments between scheduled visits may arrange an Unscheduled Visit (same procedures as mid-Week 1 Unscheduled Visit described above).

Table 3:Schedule of Assessments

												0	pen I	abel	Trea	tmen	t Peri	iod											u	low- 1p riod
Visit ^a	1 ^b	2 [°]	3	4	5	6	7	8	9	10	11	12	13	14	15	16	17	18	19	20	21	22	23	24	25	26	27	28/ ET/ EOT	29 ^d	30
Study week	-	1	2	4	6	8	10	12	14	16	18	20	22	24	26	28	30	32	34	36	38	40	42	44	46	48	50	52	54	56
Informed Consent	х																													
Eligibility Criteria	x																													
Pregnancy Testing ^e	х							Х						Х						Х										
Urine Drug Screen	Х																													
Weight		Х	Х	Х	Х	Х		Х		Х		Х		Х		Х		Х		Х		Х		Х		Х		Х		Х
Waist Circum- ference		Х	х	х	х	Х		Х		Х		Х		Х		Х		Х		Х		Х		Х		Х		Х		X
Vital Signs ^g		Х	Х	Х	Х	X		Х		Х		Х		Х		Х		X		Х		Х		Х		Х		Х		Х
Laboratory Samples ^h				Х				Х						Х						Х								Х		
ECG				Х				Х						Х						Х								Х		
Physical Exam				X				Х						Х						Х								Х		
PANSS ⁱ				Х		Х		Х						Х						Х								Х		
CGI-S				Х		Х		Х		Х		Х		Х		Х		Х		Х		Х		Х		Х		Х		
AE ^j		Х	Х	Х	Х	Х	Х	Х	Х	Х	Х	Х	Х	Х	Х	Х	Х	Х	Х	Х	Х	Х	Х	Х	Х	Х	Х	Х	Х	Х
ConMed ^j		Х	Х	Х	Х	Х	Х	Х	Х	Х	Х	Х	Х	Х	Х	Х	Х	Х	Х	Х	Х	Х	Х	Х	Х	Х	Х	Х	Х	Х
C-SSRS ^k		Х	Х	Х	Х	Х	Х	Х	Х	Х	Х	Х	Х	Х	Х	Х	Х	Х	Х	Х	Х	Х	Х	Х	Х	Х	Х	Х	Х	Х

Table 3:Schedule of Assessments (Continued)

												Ор	en La	abel T	reati	ment	Perio	d											Foll u Per	р
Visit ^a	1 ^b	2°	3	4	5	6	7	8	9	10	11	12	13	14	15	16	17	18	19	20	21	22	23	24	25	26	27	28/ ET/ EOT	29 ^d	30
Study week	-	1	2	4	6	8	10	12	14	16	18	20	22	24	26	28	30	32	34	36	38	40	42	44	46	48	50	52	54	56

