14.5. Efficacy Analysis

Efficacy analyses will be carried out using the FAS Population. The following endpoints will be used to evaluate durability of treatment effect:

- Change from Baseline in PANSS total score and subscales by visit
- Change from Baseline in CGI-S by visit
- PANSS response
- Relapse
- Remission
- Time to discontinuation

The PANSS (total and subscale scores) and CGI-S scores, and appropriate changes from Baseline, will be summarized using descriptive statistics. Positive and Negative Syndrome Scale response and remission at each visit will be summarized as number and percentage.

The discontinuation rate and the relapse rate will be estimated using the Kaplan-Meier (KM) Method and the KM plot will be provided.

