3.2.2. Efficacy Population

The Full Analysis Set (FAS) will include all subjects in the Safety Population who have at least one postbaseline PANSS assessment.

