3.8. Efficacy Analyses

3.8.1. General Considerations

All statistical analysis will be performed at the 5% significance level. All confidence intervals (CI) will be 2-sided 95% confidence intervals. Efficacy analysis will be carried out using the FAS population. PANSS total and subscale scores, CGI-S, PANSS response analyses and body weight will be based on both observed data and the LOCF (last observation carried forward) imputation, that is, the last observed non-missing postbaseline value will be carried forward for missing postbaseline assessments.

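### Time to discontinuation is analysed in the FAS, so treated subjects who stop without a postbaseline PANSS drop out of the curve and the Week-52 all-cause rate is too low whenever there are any

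*SAP*

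**What the plan says.** Three places assign the population. Protocol 14.5 states "Efficacy analyses will be carried out using the FAS Population" and lists time to discontinuation among the endpoints below that sentence. SAP 3.8.1 repeats the rule: "Efficacy analysis will be carried out using the FAS population". SAP 3.8.2 opens its endpoint list with "The following endpoints will be used to evaluate durability of treatment effect and summarized by treatment sequence and overall for FAS population", and time to discontinuation is the last item.

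SAP 3.2.2 defines the set: "The Full Analysis Set (FAS) will include all subjects in the Safety Population who have at least one postbaseline PANSS assessment". In Protocol Table 3 the PANSS row is marked at Weeks 4, 8, 12, 24, 36 and 52, the last column also serving as the early termination (ET) visit.

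The endpoint uses no PANSS data. For a subject who stops prematurely it is the "time from the date of first dose of study drug to the date of last dose of study drug". On estimation the SAP says "Time to treatment discontinuation will be analyzed similarly using the Kaplan-Meier method by treatment sequence and overall", covering both all-cause discontinuation and discontinuation due to AE, and on censoring "Other subjects will be censored at the last dose of the study drug". That paragraph names no other population.

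**The concern.** A PANSS requirement decides who enters an analysis of stopping, and stopping early is what prevents the PANSS from being obtained. The subjects at risk of exclusion are mainly those who stop before Week 4 and give no PANSS at an ET visit. A smaller group misses the Week-4 PANSS, stops later, and also has no ET PANSS. Exclusion therefore depends on the outcome.

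For the all-cause curve the excluded subjects are all events, so the Week-52 rate is understated. It will also differ from the discontinuation count in the disposition table. The curve is planned by treatment sequence as well, where one excluded subject weighs more. The study's stated purpose is long-term safety and tolerability, and stopping bears on it directly.

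**Working it through.** **Inputs from the documents.** N is about 390 (SAP Section 2, the expected maximum roll-over, not a calculated size). The first scheduled postbaseline PANSS is at Week 4 (Protocol Table 3). In the all-cause analysis only completers are censored, at about Week 52. The plan states no discontinuation rate and no ET PANSS completion, so there is no figure to reproduce and every size below rests on assumptions.

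**Direction at Week 52.** Let D be the premature discontinuations and k those with no postbaseline PANSS.

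- Safety Population: 1−KM(52) = D/N
- FAS: 1−KM(52) = (D−k)/(N−k)
- Shortfall: k(N−D)/[N(N−k)], positive whenever k > 0 and D < N

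A direct Kaplan-Meier calculation in 1,000 simulated data sets (N = 390, k from 1 to 40, D about 15% to 70%) gave a lower FAS rate in every one and matched these formulas to rounding error.

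**Size, with only pre-Week-4 stoppers excluded.** Assume Week-52 discontinuation D of 25%, 35% or 45% (now as a fraction of N); a first-month hazard m = 1, 2 or 3 times the later hazard; and an ET PANSS from a share q = 50%, 70% or 90% of stoppers. Then:

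- later weekly hazard h = −ln(1−D)/(4m+48)
- stopped by Week 4: W4 = 1−exp(−4mh)
- excluded fraction x = W4(1−q)
- FAS Week 52 = (D−x)/(1−x); FAS Week 4 = (W4−x)/(1−x)

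Central case (35%, m = 2, q = 70%): h = −ln(0.65)/56 = 0.00769; W4 = 1−exp(−8 × 0.00769) = 0.0597; x = 0.0597 × 0.3 = 0.0179, or 7 of 390. FAS Week 52 = (0.35−0.0179)/(1−0.0179) = 33.8%, against 35.0%. FAS Week 4 = (0.0597−0.0179)/(1−0.0179) = 4.3%, against 6.0%. For scale, the 95% sampling half-width at Week 52 is 1.96 × sqrt(0.35 × 0.65/390) = 4.7 points.

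| ET PANSS obtained | Week-52 rate too low by (points) |
|---|---|
| 90% | 0.2 to 0.6 |
| 70% | 0.5 to 1.9 |
| 50% | 0.8 to 3.3 |

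Over all combinations, 1 to 22 subjects are excluded and the Week-4 rate is too low by 0.2 to 5.3 points. With no first-month excess (m = 1), 1 to 9 are excluded and the Week-52 shortfall is 0.2 to 1.3 points.

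**Later stoppers.** If each scheduled PANSS is missed independently with probability 5% or 10%, stoppers after Week 4 add 0.04 to 0.9 excluded subjects. The Week-52 range becomes 0.2 to 3.4 points; the Week-4 range stays 0.2 to 5.3.

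**Before Week 52 the direction is usual, not certain.** Take 23 of 390 stopped by Week 4 (5.90%). If the only exclusions are 5 later stoppers, Week 4 becomes 23/385 = 5.97%, slightly too high, while Week 52 still falls from 137/390 = 35.1% to 132/385 = 34.3%. If one early stopper is excluded as well, Week 4 is 22/384 = 5.73%. Outweighing that one would take 16 later exclusions (22/373 = 5.898% against 23/390 = 5.897%).

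**By sequence.** Assume 130 subjects and 46 stops (35.4%). One exclusion gives 45/129 = 34.9%, 0.5 points lower; the same exclusion overall at 35% costs 0.17 points. Five exclusions give 41/125 = 32.8%.

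**Discontinuation due to AE.** Here the direction depends on why the excluded subjects stopped. In one simulated example with 156 stops and 12 exclusions, Safety and FAS rates were both 11.9% if none of the 12 stopped for an AE, and 14.6% against 11.9% if all did.

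**The case against.** The route to exclusion is narrow. Protocol 7.3 has the ET visit repeat the Visit 28 assessments, which include PANSS, so most early stoppers should qualify. For those who do not return it requires an attempt by telephone to collect safety and efficacy parameters, and PANSS is one of only two efficacy scales. The number excluded could be zero.

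Most of the missing information is also planned elsewhere. SAP 3.3 reports Safety and FAS counts together with discontinuations and reasons. If everyone outside the FAS is a stopper, a reader can recover the Week-52 figure from S_Safety(52) = S_FAS(52) × (N−k)/N. SAP 3.7.2 summarises duration of dosing, and SAP 3.9 covers AEs leading to discontinuation, both in the Safety Population. The study is single-treatment and descriptive, no test between sequences is planned for this endpoint, and Protocol and SAP agree with each other. The largest shortfalls need 45% discontinuation, a threefold early hazard and 50% ET PANSS all at once.

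These points limit the size and the consequence, and they stand to that extent. They do not remove the error. The protocol itself foresees subjects who fail or refuse to return, and it neither provides for nor rules out a PANSS by telephone. Recovering one Week-52 number by hand does not supply the curve, whose early weeks are the most affected. Agreement between the two documents does not justify an outcome-dependent exclusion.

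**Conclusion.** The concern holds. The population assignment is explicit, and the Week-52 direction for the all-cause rate follows from algebra once any treated stopper lacks a postbaseline PANSS and at least one subject completes. The size cannot be known from the documents: about 0.2 to 3.4 points at Week 52 under the assumptions above, 1.2 points in the central case, roughly a quarter of the sampling half-width. Confidence is high for the direction and not for the size.

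This sits at the low end of what should be fixed. It affects one descriptive display and no decision rule, but the correction is a matter of wording.

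**What to change.** In SAP 3.8.2, take time to discontinuation out of the list headed by the FAS and state: *Time to discontinuation (all-cause and due to AE) will be analysed in the Safety Population; the FAS analysis will be a sensitivity analysis.* Note the exception in SAP 3.8.1 so that its general FAS rule does not contradict it. SAP 3.7.2 already uses the Safety Population for duration of dosing, which rests on the same two dates. In SAP Section 5, record the departure from Protocol 14.5.

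The cost is a few sentences, with no new data and no new method. If no subject was excluded, the result is unchanged; otherwise the reported Week-52 all-cause rate rises.

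Optional and separate from this point: because other discontinuations are censored, 1−KM for discontinuation due to AE should not be read as the proportion stopping for AEs. A cumulative incidence function with other discontinuations as competing events could be added.

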Abnormal Movement Scales				x				х						X						X								Х		
IWQOL	Х			Х				Х						Х						Х								Х		
EQ-5D	Х			Х				Х						Х						Х								Х		
Cigarette Use	Х			X				Х						х						х								Х		
Emergency Treatment Card ^m	X	Х	х	х	x	х	Х	X	Х	X	X	X	Х	Х	Х	Х	Х	Х	Х	Х	Х	Х	Х	Х	X	Х	X	Х		
Study Drug Dispensation	Х	Х	Х	Х	X	Х	Х	Х	Х	Х	х	х	Х	х	Х	х	Х	х	х	х	х	Х	х	х	х	х	х			
Study Drug Adherence Review ⁿ		Х	х	x	x	х	Х	х	Х	х	x	х	Х	х	X	X	X	X	X	X	X	Х	X	х	X	X	X	Х		

Abbreviations: AE=adverse event; CGI-S=Clinical Global Impression-Severity; ConMed=concomitant medication; C-SSRS=Columbia-Suicide Severity Rating Scale; ECG=electrocardiogram; EOT=End of Treatment; EQ-5D=EuroQOL-5D; IWQOL=Impact of Weight on Quality of Life; PANSS=Positive and Negative Syndrome Scale

^a A visit window of ±2 days is permitted throughout the Treatment Period and the Follow-up Period (Visits 2-30)

^b Visit 1 must occur within 7 days of the EOT Visit (Visit 6) of the antecedent study, ALK3831-A305, and may occur on the same day. Assessments from ALK3831-A305 Visit 6 will constitute the Baseline/Screening assessments for this extension study

^c On Day 3, study staff will contact outpatient subjects by phone to determine if a dose increase to ALKS 3831 15/10 or 20/10 is needed. An Unscheduled Interim Visit will be arranged for subjects requiring a dose adjustment for study drug return and adherence review and study drug dispensation. Any subsequent dose adjustments throughout the study require subjects to come to the site for either a scheduled or unscheduled visit

^d Follow-up Visits (Visits 29 and 30) are not required for subjects who enroll in ALK3831-A308

^e Urine pregnancy test prior to dosing at Visit 1 and at all subsequent specified visits

Protocol ALK3831-A306 v 3.0 (Amendment 2.0)

- ^f Urine drug screen via dipstick prior to dosing on Day 1 for subjects who did not receive a urine drug screen at Visit 6 of the ALK3831-A305 study, or for subjects for whom Visit 1 of this study is not the same day as Visit 6 of the ALK3831-A305 study. Urine drug screen includes opiates, phencyclidine (PCP), amphetamine/methamphetamine, and cocaine
- ^g Vital signs include orthostatic blood pressure and heart rate, respiratory rate, and oral body temperature. Blood pressure, pulse rate, and respiratory rate will be taken after the subject has been supine for 5 minutes and once again after the subject has stood for 2 minutes

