APPENDIX B. POSITIVE AND NEGATIVE SYNDROME SCALE

Positive Scale (P)

P1. Delusions. Beliefs which are unfounded, unrealistic, and idiosyncratic. Basis for rating: thought content expressed in the interview and its influence on social relations and behavior as reported by primary care workers or family.

	Rating	Criteria
1	Absent	Definition does not apply.
2	Minimal	Questionable pathology; may be at the upper extreme of normal limits.
3	Mild	Presence of one or two delusions, which are vague, uncrystallized, and not tenaciously held. Delusions do not interfere with thinking, social relations, or behavior.
4	Moderate	Presence of either a kaleidoscopic array of poorly formed, unstable delusions or a few well-formed delusions that occasionally interfere with thinking, social relations, or behavior.
5	Moderate	Presence of numerous well-formed delusions that are tenaciously held and occasionally interfere with thinking, social relations, or behavior.
6	Severe	Presence of a stable set of delusions which are crystallized, possibly systematized, tenaciously held, and clearly interfere with thinking, social relations, and behavior.
7	Extreme	Presence of a stable set of delusions which are either highly systematized or very numerous, and which dominate major facets of the patient's life. This frequently results in inappropriate and irresponsible action, which may even jeopardize the safety of the patient or others.

Positive Scale (P)

P2. Conceptual disorganization. Disorganized process of thinking characterized by disruption of goal-directed sequencing, e.g., circumstantiality, tangentiality, loose associations, non-sequiturs, gross illogicality, or thought block. *Basis for rating*: cognitive-verbal processes observed during the course of interview.

	Rating	Criteria
1	Absent	Definition does not apply.
2	Minimal	Questionable pathology; may be at the upper extreme of normal limits.
3	Mild	Thinking is circumstantial, tangential, or paralogical. There is some difficulty in directing thoughts toward a goal, and some loosening of associations may be evidenced under pressure.
4	Moderate	Able to focus thoughts when communications are brief and structured, but becomes loose or irrelevant when dealing with more complex communications or when under minimal pressure.
5	Moderate Severe	Generally has difficulty in organizing thoughts, as evidenced by frequent irrelevancies, disconnectedness, or loosening of associations even when not under pressure.

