P6. Suspiciousness/persecution. Unrealistic or exaggerated ideas of persecution, as reflected in guardedness, a distrustful attitude, suspicious hypervigilance, or frank delusions that others mean one harm. *Basis for rating:* thought content expressed in the interview and its influence on behavior as reported by primary care workers or family.

	Rating	Criteria
1	Absent	Definition does not apply.
2	Minimal	Questionable pathology; may be at the upper extreme of normal limits.
3	Mild	Presents a guarded or even openly distrustful attitude, but thoughts, interactions, and behavior are minimally affected.
4	Moderate	Distrustfulness is clearly evident and intrudes on the interview and/or behavior, but there is no evidence of persecutory delusions. Alternatively, there may be indication of loosely formed persecutory delusions, but these do not seem to affect the patient's attitude or interpersonal relations.
5	Moderate Severe	Patient shows marked distrustfulness, leading to major disruption of interpersonal relations, or else there are clear-cut persecutory delusions that have limited impact on interpersonal relations and behavior.
6	Severe	Clear-cut pervasive delusions of persecution which may be systematized and significantly interfere in interpersonal relations.
7	Extreme	A network of systematized persecutory delusions dominates the patient's thinking, social relations, and behavior.

Positive Scale (P)

P7. *Hostility.* Verbal and nonverbal expressions of anger and resentment, including sarcasm, passive-aggressive behavior, verbal abuse, and assaultiveness. *Basis for rating:* interpersonal behavior observed during the interview and reports by primary care workers or family.

	Rating	Criteria
1	Absent	Definition does not apply.
2	Minimal	Questionable pathology; may be at the upper extreme of normal limits.
3	Mild	Indirect or restrained communication of anger, such as sarcasm, disrespect, hostile expressions, and occasional irritability.
4	Moderate	Presents an overtly hostile attitude, showing frequent irritability and direct expression of anger or resentment.
5	Moderate Severe	Patient is highly irritable and occasionally verbally abusive or threatening.
6	Severe	Uncooperativeness and verbal abuse or threats notably influence the interview and seriously impact upon social relations. Patient may be violent and destructive but is not physically assaultive toward others.

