3	Mild	Conversation shows little initiative. Patient's answers tend to be brief and unembellished, requiring direct and leading questions by the interviewer.
4	Moderate	Conversation lacks free flow and appears uneven or halting. Leading questions are frequently needed to elicit adequate responses and proceed with conversation.
5	Moderate Severe	Patient shows a marked lack of spontaneity and openness, replying to the interviewer's questions with only one or two brief sentences.
6	Severe	Patient's responses are limited mainly to a few words or short phrases intended to avoid or curtail communication. (E.g., "I don't know," "I'm not at liberty to say.") Conversation is seriously impaired as a result, and the interview is highly unproductive.
7	Extreme	Verbal output is restricted to, at most, an occasional utterance, making conversation impossible.

Negative Scale (N)

N7. Stereotyped thinking. Decreased fluidity, spontaneity, and flexibility of thinking, as evidenced in rigid, repetitious, or barren thought content. *Basis for rating:* cognitive-verbal processes observed during the interview.

	Rating	Criteria
1	Absent	Definition does not apply.
2	Minimal	Questionable pathology; may be at the upper extreme of normal limits.
3	Mild	Some rigidity shown in attitudes or beliefs. Patient may refuse to consider alternative positions or have difficulty in shifting from one idea to another.
4	Moderate	Conversation revolves around a recurrent theme, resulting in difficulty in shifting to a new topic.
5	Moderate Severe	Thinking is rigid and repetitious to the point that, despite the interviewer's efforts, conversation is limited to only two or three dominating topics.
6	Severe	Uncontrolled repetition of demands, statements, ideas, or questions which severely impairs conversation.
7	Extreme	Thinking, behavior, and conversation are dominated by constant repetition of fixed ideas or limited phrases, leading to gross rigidity, inappropriateness, and restrictiveness of patient's communication.

General Psychopathology Scale (G)

G1. Somatic concern. Physical complaints or beliefs about bodily illness or malfunctions. This may range from a vague sense of ill being to clear-cut delusions of catastrophic physical disease. *Basis for rating:* thought content expressed in the interview.

	Rating	Criteria
1	Absent	Definition does not apply.
2	Minimal	Questionable pathology; may be at the upper extreme of normal limits.

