3. DATA ANALYSIS

3.1. General Statistical Methodology

Baseline for efficacy or safety analysis is defined as the last non-missing assessment before the first dose of ALKS 3831 in ALK3831-A306 study, and it will be used for all efficacy and safety analysis unless specified otherwise.

Antecedent study baseline, defined as the last non-missing assessment on or before the first dose of study drug during double-blind treatment period in ALK3831-A305 study, may be explored as applicable.

Treatment sequence is defined according to the treatment assignment in antecedent and current studies as ALKS 3831/ALKS 3831 (ALKS 3831 in both ALK3831-A305 study and ALK3831-A306 study), OLZ/ALKS 3831 (olanzapine in ALK3831-A305 study and ALKS 3831 in ALK3831-A306 study), or PBO/ALKS 3831 (placebo in ALK3831-A305 study and ALKS 3831 in ALK3831-A306 study).

In general, descriptive statistics: n, mean (\pm standard deviation [SD]), median, minimum, and maximum, for continuous variables and number and percentage of subjects in each category for categorical variables will be provided.

All statistical tests and confidence intervals (CIs), unless stated otherwise, will be 2-sided and will be set at an alpha level of 0.05.

All source data will be presented as subject data listings.

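### PANSS response is a 30% fall in a total whose minimum is 30, so the effective threshold varies with baseline and cannot be met from a baseline of 42 or below

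*SAP*

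**What the plan says.** SAP 3.8.2 includes among the efficacy endpoints "Proportion of Subjects with PANSS response ($\geq 30\%$ improvement from baseline in PANSS total score". It gives no formula. Protocol 14.5 names PANSS response without defining it.

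The reference value is set in SAP 3.1: "Baseline for efficacy or safety analysis is defined as the last non-missing assessment before the first dose of ALKS 3831 in ALK3831-A306 study". The Protocol's footnotes to the schedule of assessments (8.2) say where that value comes from: "Assessments from ALK3831-A305 Visit 6 will constitute the Baseline/Screening assessments for this extension study". Baseline is therefore the end of four weeks of treatment in A305. The A305 baseline is mentioned in SAP 3.1 only as something that "may be explored as applicable".

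Protocol Appendix B prints the scale. The lowest rating on every item is 1, labelled "Absent Definition does not apply"; there is no zero.

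Response is tabulated by treatment sequence and overall (SAP 3.8.2), on observed and LOCF data (SAP 3.8.1), and by US versus non-US region (SAP 3.8.3.1).

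**The concern.** A percentage change is easy to interpret only when zero on the scale means none of the thing measured. Here the total cannot go below 30, so 30 points that no subject can lose sit in the denominator. The label 30% then stands for a different proportion of symptoms in each subject, and for the mildest subjects it stands for a score that does not exist.

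This matters more in an extension than in an acute study, because baseline is taken after treatment has begun to work. The SAP also splits response by sequence (ALKS 3831, olanzapine or placebo in A305). If those groups enter at different PANSS levels, part of any difference in their response rates may come from the rule rather than from what happened in A306.

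The SAP handles the same problem elsewhere: in 3.8.3 the IWQOL-Lite scores are rescaled by the test score range, which removes that scale's non-zero minimum.

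**Working it through.** The plan has no figure of its own to reproduce: SAP section 2 says that no formal sample size calculation was done, and 30% is a definition.

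**Inputs from the documents.** Appendix B has 7 positive items (P1-P7), 7 negative items (ending with "N7. Stereotyped thinking") and 16 general items (G1-G16), each rated 1 to 7.

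- Minimum total: (7 + 7 + 16) x 1 = 30
- Maximum total: 30 x 7 = 210

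**When the literal rule can be met.** With baseline B and visit score S, the rule is (B - S)/B >= 0.30. The largest possible fall is B - 30, so (B - 30)/B >= 0.30 is needed, which gives B >= 30/0.7 = 42.86. Totals are integers:

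- B = 42: S must be at most 29.4, below the minimum. Impossible, as for every total from 30 to 42.
- B = 43: S must be at most 30.1, so every item must be rated 1.

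**Share of removable points required**, 0.30B/(B - 30), and points needed on each rule:

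| Baseline | Raw rule: points | Share of B - 30 | Floor-corrected: points |
|---|---|---|---|
| 50 | 15 | 15/20 = 75% | 6 |
| 60 | 18 | 18/30 = 60% | 9 |
| 80 | 24 | 24/50 = 48% | 15 |
| 100 | 30 | 30/70 = 43% | 21 |
| 120 | 36 | 36/90 = 40% | 27 |

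The corrected rule, (B - S)/(B - 30) >= 0.30, asks for 30% of the removable points at every baseline above 30.

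**Size (assumed inputs).** The documents give no entry PANSS. The assumptions are a normal baseline with mean 60-75 and SD 10-12, an independent normal change with mean -6 to -8 and SD 9-10, and scores rounded and held at 30 or above. Simulation over this grid gives:

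- Response, raw rule: about 4% to 16%
- Response, floor removed: about 22% to 46%
- Baseline 42 or below: about 0% to 7%, or up to about 27 of the planned 390 (0.07 x 390)

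With a larger mean change of -12 at entry mean 65, the figures are about 21-23% and 56%.

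**Between sequences, two models of change.**

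- *Equal proportional improvement.* Every subject loses on average 35% (SD 30%) of the points above 30. The raw rule gives about 19% response at entry mean 60 and 32% at 80. The corrected rule gives 57% at both.
- *Change unrelated to baseline.* Mean -8 (SD 10), baseline SD 12. The raw rule gives about 13% at entry mean 65 and 7% at 80. The corrected rule gives about 41% and 26%.

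**False positives.** With no mean change (SD 9-10) at entry means 60-75, the corrected rule labels about 8-20% of subjects responders, against 1-4% on the raw rule.

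**The case against.** **The definition is explicit, and any responder cut-off is a convention.** This stands in part. A reader might infer that the raw rate is wrong or understated, but the documents name no target that it misses; it is a stricter criterion than the corrected one. What remains is that the strictness varies with baseline, and that for some possible baselines no outcome qualifies.

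**The direction of distortion is not established.** This stands. It is tempting to say that the rule penalises the sequences that improved most in A305. As a share of removable points it does; in points it asks less of milder subjects (18 at 60, 24 at 80). When change is unrelated to baseline, the milder group shows the higher raw rate, and the correction widens the gap from about 6 to 15 points (though the ratio falls from about 1.9 to 1.6). Different entry levels across sequences are also only an assumption.

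**The SAP does not say that many subjects will enter with low totals.** This stands. A reader might take the limit of 80 in the stabilization definition as an expectation. It is one condition for analysing relapse and remission, and no expected proportion is given.

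**The corrected rule has a cost.** This stands. At a baseline of 33 a fall of one point counts as response, and at 42 a fall of four. The false-positive figures above show the effect.

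**The consequence is limited, and the formula may be settled elsewhere.** Change in PANSS total, subscales and CGI-S is reported by visit, and remission uses absolute item scores. The programming specifications are a separate document not available here; if they already remove the floor, the SAP should say so.

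**Conclusion.** The point holds. On the SAP's text, response cannot occur at a baseline of 42 or below, and the required share of removable symptoms falls from 75% at baseline 50 to 43% at 100. These results follow from Appendix B and SAP 3.8.2 alone.

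The response rates, the 0-7% of subjects at 42 or below and the between-sequence examples rest on assumed entry scores and changes. They show that the choice of denominator can move the reported rate severalfold and can create or alter a difference between sequences; they do not predict the trial's result.

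The documents do not support a reading that this threatens the study's conclusions. The objective is long-term safety and tolerability, the study is open-label and not randomized, and response is one descriptive efficacy summary among several. No primary conclusion, alpha or power changes. The change is worth making because the rule misbehaves in the range of scores that subjects may well have after four weeks of treatment, and because the remedy is small.

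**What to change.** In SAP 3.8.2:

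1. Define response as 100 x (baseline total - visit total)/(baseline total - 30) >= 30%, using the A306 baseline, for both the observed and the LOCF tables.
2. Exclude subjects with a baseline of exactly 30 from the denominator, because the formula is undefined there.
3. Report the raw-total version beside it as a labelled row.
4. Report, by sequence and overall, the number of subjects with a baseline of 42 or below, who cannot respond on the raw rule.

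The cost is a line of SAP wording, one derived variable, one extra row and one count. Because the corrected rule counts small fluctuations as response at low baselines, neither row should be quoted without the other. The raw row also keeps a comparison with A305 possible if that study used the raw total.
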